5.9. RANDOMIZATION

Randomization will occur at the ward level. Groups of two consecutive wards will be randomized to one of the two arms.

The investigators will be aware of the assigned IC strategy in order to monitor implementation of each strategy. Data analysts will be unaware of the IC strategy assignment.

5.10. ENDPOINTS AND OUTCOMES

5.10.1. PRIMARY ENDPOINT

Incidence density of colonization with ESBL-E across the study periods.

- The primary outcome is the nosocomial ESBL-E-acquisition rate per 1,000 patient days. Acquisition of ESBL-E-carriage is defined as recovery of ESBL-E isolates from clinical and/or rectal screening specimens >3 days after hospital admission (admission day = day 1) from patients with negative admission screening results. If a patient is discharged from the ward and re-admitted to the ward on the same or the following day, then the discharge will be ignored in the primary analysis. If the readmission occurs later, the patient will be treated as a new case.

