Primary Hypothesis and Outcome	If all ESBL-E-carriers are identified through universal surveillance screening, Contact Isolation (CI) will not reduce incidence densities of ESBL-E-acquisition among patients in medical and surgical wards when compared to SP. The primary outcome is the ESBL-E acquisition rate per 1,000 patient days. Acquisition of ESBL-E-carriage is defined as recovery of ESBL-E isolates from clinical and/or rectal/perianal/stool screening specimens >3 days after admission (admission day = day 1) from patients with negative admission screening results. If a patient is discharged from the ward and re-admitted to the ward on the same or the following day, then the discharge will be ignored in the primary analysis. If the readmission occurs later, the patient will be treated as a new case.
Secondary Hypotheses	
 1. Healthcare workers (HCWs) will not practice HH more frequently during contact with known ESBL-E-carriers in CI than in SP 2. HCWs will practice HH more frequently during contact with known ESBL-E-carriers than with patients not known to be ESBL-E-carriers
Secondary Outcomes	The trial will assess the efficacy of the CI strategy in reducing the incidence density of colonization with ESBL-E by the methods described above. In addition, the trial will evaluate the efficacy of the CI strategy in reducing the cumulative incidence of ESBL-E infections as determined by laboratory-based surveillance of clinical culture results. The trial will evaluate the frequency of hand hygiene and the use of gloves and gowns by HCWs, as assessed by bedside observations of a trained monitor. The antibiotic use will be analysed for all patients in defined daily doses (DDD) preferably weekly/at least monthly. In a subset of ESBL-E-patients antibiotic use will also be analysed at patient level in days of therapy (DOT). The trial will evaluate the consumption of alcohol-based handrub (ABHR) per patient days to evaluate differences between ESBL-E-carriers and Non-ESBL-E-patients as well as differences between the two IC strategies. Because the interventions involve minimal risk, no specific safety measures will be made.
Study Design	The study is a two-arm, cluster-(Non-ICU) randomized, controlled study (cRCT) of two IC strategies with cross-over design, which will be performed in different European countries. Randomization will be performed at the ward level. Primary analyses will be performed at the ward level.

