5.5. SURVEILLANCE CULTURES

In both arms of the trial, wards will collect surveillance cultures to identify patients who are colonized with ESBL-E using the same procedures. The results of the surveillance cultures will be reported back to the wards immediately in both arms of the trial.

All patients will be screened at admission (admission day = day 1) to the ward or as soon as possible within 3 days. Repeated surveillance cultures will be obtained for patients staying longer than 7 days on a specific day each week (i.e., every Wednesday, Friday etc.). Patients discharged from the ward will have samples obtained on the day of discharge, if possible, or the day before. Patients readmitted to the ward will be treated as new cases.

The procedures for obtaining and processing swabs are outlined in Section 6.4. (SURVEILLANCE CULTURES).

Surveillance cultures will be obtained by the ward nurses and/or research personnel.

All specimens will be processed by the institutional microbiology laboratories. In all wards, clinicians may order microbiological cultures at any time for clinical indications. All results will be reported as soon as possible to the wards. ESBL-E-isolates will be sent to the microbiologic laboratory of the Hospital Ramon y Cajal in Madrid (SERMAS) for further molecular epidemiologic analysis.

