6.3. PATIENT DATA (ANNEX III WP5 DF3 ESBL-E PATIENT)

The following data will be only obtained from patients who are ESBL-E-positive (“Cases”)

Data	Collected by	
	Local study personnel	Ward personnel
Known ESBL-E patient at admission (Yes / No) ¹	X	
Day of admission (Day of study) ¹	X	
Day of discharge (Day of study) ¹	X	
Day of finding (Day of study) ¹	X	
Reason for sampling (Screening/ Clinical/ No sample) ^d	X	
Sample: ESBL-E (Positive: E. coli; Klebsiella; other/ Negative / No data) ^d	X	
Pos. Result known (documented in patient file on the ward) (Yes / No / Known ESBL-E) ^d	X	
Contact Precautions (CI 1-4 / SP 1-4 / No data) ^d	X	
ESBL-E Infection (No / Yes ___) ^d	X	
Handrub Consumption (ml / day) ^d	X	
Antibiotic Use (Yes / No ___, if yes, type of antimicrobial substance ___) ^{d,e}	X	
x ¹ once x ^a annually x ^m monthly x ^d daily x ^e in a subset of patients		

If a patient is ESBL-E-positive for the first time during the study these data should be filled in retrospectively preferably from the day of admission onwards, but at least for the 6 days prior to the first ESBL-E result.

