4. SAMPLES: TYPE AND COLLECTING TIME

-In both arms of the trial, rectal swabs will collect for surveillance cultures in order to identify patients who are colonized with ESBL-E.

-All patients will be screened:

- a) At admission (day 1) to the ward or as soon as possible within 3 days.
- b) Repeated surveillance cultures will be obtained for patients staying longer than 7 days on a specific day each week (i.e., every Wednesday, Friday etc.).
- c) At patient discharge from the ward: on the same day of discharge, if possible, or the day before.

-Patients readmitted to the ward will be treated as new cases.

-All specimens will be processed in the institutional microbiology laboratory and results will be reported as soon as possible to the wards

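### The primary endpoint is timed from hospital admission although the negative screen it relies on is timed from ward admission, and its wording does not exclude patients already known to carry ESBL-E

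*Protocol*

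**What the plan says.** **Endpoint.** Protocol section 5.10.1 counts ESBL-E recovered from "clinical and/or rectal screening specimens >3 days after hospital admission (admission day = day 1) from patients with negative admission screening results". The synopsis gives the same rule with a longer specimen list and without saying which admission is meant: "clinical and/or rectal/perianal/stool screening specimens >3 days after admission (admission day = day 1) from patients with negative admission screening results".

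**Admission screen.** Section 5.5 starts the clock on the ward: "All patients will be screened at admission (admission day = day 1) to the ward or as soon as possible within 3 days". Section 4 of the microbiological protocol agrees: "At admission (day 1) to the ward or as soon as possible within 3 days".

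**Readmission.** Sections 5.5 and 4 state without qualification: "Patients readmitted to the ward will be treated as new cases". Section 5.10.1 and the synopsis disregard, for the primary analysis, a discharge followed by return on the same or next day. A later return starts a new case. Nothing is said about a patient who was positive in the earlier stay.

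**Data.** The patient form in section 6.3 records "Known ESBL-E patient at admission (Yes / No") and a single date, "Day of admission (Day of study"), without saying whether it is the hospital or the ward date. The form is completed only for ESBL-E-positive patients.

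**The concern.** Randomization and the primary analysis are at ward level, so the endpoint should count carriage that the ward's strategy could have prevented. The stated rule can admit two kinds of event that it could not.

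- **Transfers.** Take a patient who reaches the ward on hospital day 6, swabs negative on ward day 1 and is positive on ward day 2. On the hospital clock this is a ward acquisition. On the ward clock it is not.
- **Existing carriers.** A known carrier with one negative admission swab and a later positive meets every condition in section 5.10.1. So does a patient who was positive in an earlier study stay and returns after more than a day. In the contact isolation phase, section 5.3 isolates the known carrier as a source; the endpoint rule could count the same patient as a new acquisition.

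Such events occur under both strategies and dilute a real difference. The primary hypothesis is that contact isolation will not reduce acquisition, so the dilution favours the trial's own hypothesis. Sites working from different sections could also count different events.

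**Working it through.** **1. The plan's own figure.** Section 9.1 assumes 0.8 acquisitions per 100 patients, a 50% reduction, two-sided alpha 0.05 and 80% power. The two-proportion formula with continuity correction gives 6,341 per phase, against 6,343 stated. Then 6,343 × 2.9 = 18,394.7, and 1 + 634 × 0.003 = 2.90. Both match, so no arithmetic error is involved here.

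**2. The two clocks.** Hospital admission never falls after ward admission, so every ward-clock event is also a hospital-clock event. The hospital clock adds only transferred patients who turn positive in their first few ward days after a negative ward swab. Weekly swabs apply only to stays over 7 days, so these events need a clinical culture or a discharge swab after a short stay. The documents give no transfer share, and this part cannot be sized.

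**3. Known carriers: inputs.**

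| Input | Value | Source |
|---|---|---|
| Patients | 39,528, or 19,764 per strategy | Section 9.1 |
| True acquisitions, standard precautions | 19,764 × 0.008 = 158.1 | Section 9.1 |
| True acquisitions, contact isolation | 19,764 × 0.004 = 79.1 | Section 9.1 |
| Carriage | 3-7% | Section 3 |
| False-negative admission swab | 10% | Assumed |
| Carriers already known | 25-50% | Assumed |
| Positive again later in the stay | 30-50% (extreme: 100%) | Assumed |

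**4. Formula.** Spurious events x = 39,528 × carriage × 0.10 × share known × re-detection, split equally between strategies. Observed IDR = (79.1 + x/2) / (158.1 + x/2). Patient-days are taken as equal in the two phases.

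| Case | x | Observed IDR |
|---|---|---|
| 3%, 25% known, 30% re-detected | 8.9 | 83.5/162.6 = 0.51 |
| 7%, 50% known, 50% re-detected | 69.2 | 113.6/192.7 = 0.59 |
| 3%, 25% known, all re-detected | 29.6 | 93.9/172.9 = 0.54 |
| 7%, 50% known, all re-detected | 138.3 | 148.2/227.3 = 0.65 |

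**5. Power.** Take the design effect at face value (6,343 effective patients per arm) and use a test without continuity correction. Power is 83% with no spurious events. With 0.0225 spurious events per 100 patients (first row) it is 82%; with 0.175 per 100 (second row) it is 73%.

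**6. What excluding known carriers leaves.** Carriers not known at admission (50-75% under the same assumption) also have false-negative swabs. At 3% carriage, 50% unknown and 30% re-detection, x = 17.8 and the IDR is 87.9/167.0 = 0.53. At 7%, 75% and 50%, x = 103.8 and the IDR is 130.9/210.0 = 0.62. The exclusion removes part of the bias, not all of it.

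**The case against.** **The protocol does not say that known carriers count.** A reader might infer that it deliberately includes them. It does not go that far: it fails to exclude them. The word acquisition suggests that new carriage was meant, and section 6.3 refers separately to patients positive for the first time during the study. This stands as a limit on the claim. It does not repair the rule, whose stated conditions such a patient still meets.

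**Only section 5.10.1 names a clock for the endpoint.** A reader might infer two competing endpoint definitions. Sections 5.5 and 4 time the swab, and the synopsis is compatible with either reading. A nosocomial limit counted from hospital admission can coexist with a ward-entry swab. This largely stands. What remains is a mismatch inside one definition and an unspecified date on the form.

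**The readmission sentences can be reconciled.** Those in sections 5.5 and 4 can be read as re-screening rules, with section 5.10.1 governing the analysis. That is the better reading, so this needs a clarifying sentence and is no proven contradiction. The difference in specimen lists is a minor inconsistency with no shown effect.

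**The size is assumed.** A reader might take 0.65 or more as the expected distortion. That needs every false-negative known carrier to be detected later, and no document supports it. The 0.8 per 100 is also described as incidence under regular surveillance cultures, so it may already contain such events. Both points stand.

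**Known carriers cannot simply be removed from the denominator.** The form covers only ESBL-E-positive patients, and the offset is aggregate ward patient-days. Removing only those who later test positive would condition the denominator on the outcome. This stands, and the fix is limited to the numerator.

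**Conclusion.** The point holds in a limited form. As worded, the primary endpoint combines a hospital-based time limit with a ward-based negative screen and relies on a single swab to exclude carriers, although known status is recorded. This is more than detail that could be left to an analysis plan: the stated rule, followed as written, admits events that the ward's strategy cannot prevent.

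The pull toward 1 is an inference. It requires a true effect of contact isolation and similar misclassification under both strategies. The common screening procedures and the crossover make the second condition plausible but do not guarantee it. Under the assumptions shown, a true IDR of 0.50 would be seen as about 0.51-0.59, with power between 82% and 73% instead of 83%; full re-detection would take the IDR to 0.65. None of these values can be derived from the documents. The clock contributes only through transferred patients positive in their first ward days, and its size is unknown.

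**What to change.** 1. In the synopsis and section 5.10.1, use one definition: the first ESBL-E specimen more than 3 days after admission to the study ward, in a patient with a negative ward-admission screen who was not known to be ESBL-E-positive before that admission (by the form's flag or an earlier positive study stay). Give one specimen list in both places.
2. In section 6.3, state that the admission date is the ward date, and add the hospital admission date.
3. In section 5.5 and section 4 of the microbiological protocol, state that the same- or next-day readmission rule of section 5.10.1 governs the analysis.
4. Apply the carrier exclusion to the numerator only and keep ward patient-days as the offset.
5. Report a sensitivity analysis under the definition as section 5.10.1 now words it.

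**Cost.** Slightly fewer counted events, one added date field and linkage of repeat stays, which the protocol does not describe. The flag for known carriers already exists. False-negative swabs in carriers not known at admission remain and should be acknowledged as a limitation.

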5.10.2. SECONDARY ENDPOINTS

- New events of nosocomial ESBL-E infections expressed as incidence density of nosocomial ESBL-E-infections per 1000 patient days.
 - Definitions for urinary tract infections (UTI), hospital-acquired pneumonia (HAP), blood stream infections (BSI), and surgical site infections (SSI) will be in accordance with modified CDC definitions²⁷.
- Compliance with hand hygiene and contact precautions of healthcare workers during patient care, assessed by direct observation performed by a trained monitor using a standardized observation procedure.
 - The frequency of hand hygiene and use of gloves and gowns/aprons by healthcare workers per patient contact during the intervention periods per indicated opportunities
- Aggregate data on antibiotic use at the ward level will be collected monthly, preferably in DDD per 1000 patient-days.
- Individual-level systemic antibiotic use (according to the Anatomical Therapeutic Chemical Classification System [ATC- J01]) expressed as days of therapy for known ESBL-E-carriers in a subset of patients.
- Alcohol-based handrub (AHC) consumption for known ESBL-E-carriers as well as for non-ESBL-E-patients in both intervention periods.
 - AHC for patients known to be colonized/infected with ESBL-E in ml per day (use in ESBL-E-positive patient days as known on the ward, i.e. the days the ESBL-positive result is known on the ward and after).
 - AHC for non-ESBL-E patients and unknown carriers in ml/day (median use in ESBL-E-negative patient days as known on the ward, i.e. all patient days of non-ESBL-E-patients plus all patient days of an ESBL-E-patient before the first positive result is known on the ward).
 - Total AHC on the ward in liters/month, including belt pockets and disinfection dispensers other than automated counting devices.

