Standard precautions (SP) may be as effective for limiting the spread of ESBL-E, especially when hand hygiene compliance is high¹⁷, and one study even found lower hand hygiene compliance under isolation conditions¹⁸.

Currently, many hospitals in Europe are unable to isolate patients with MDRO due to shortage of single rooms, while, the prevalence of intestinal ESBL-E-carriage among healthy people^{19, 20},²¹ and people admitted to the hospital^{22, 23} has risen sharply to 3-7 % depending on the setting and the population studied. Moreover, if ESBL-E-carriers are identified solely by cultures

obtained for clinical purposes, many asymptomatic patients colonized with ESBL-E will remain undetected and thus will not be cared for with contact precautions.

Hence, a combined approach of active surveillance screening at admission and CI of detected ESBL-E-carriers would be the logical consequence. However, this would increase the management costs for ESBL-E-patients even further.

Implementing HICPAC guideline recommendations would have considerable cost implications and impact on the quality of patient care²⁴. Therefore, adding contact precautions for the rapidly increasing number of patients colonized with ESBL-E should be based on solid evidence.

Last but not least, transmission prevention should not be considered an end in itself but rather one particular strategy to achieve the higher goal of reducing clinical infections and associated morbidity and mortality¹². This should also be investigated before final conclusions about isolation strategies for ESBL-E-patients are made.

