9.2.4. ANALYSES OF SECONDARY OUTCOMES

The incidence density of hospital-acquired infections caused by ESBL-E in the CI period with the SP period will be compared in total and ward levels. Additionally, a regression model will be performed to adjust by confounders.

The incidence density of clinical isolates with ESBL-E will be analysed by segmented regression using 31 observation months (3 month baseline, 12 month first intervention, 1 month washing out, 12 month second intervention, 3 month post intervention). Incidences of the different study phases will also be compared and tested.

To analyse the difference in HH practice for known ESBL-E patients in the two intervention periods, AHC will be calculated for ESBL-E-positive patient days (per ESBL-E-positive patient day) in both intervention periods at total and ward levels and differences will be tested.

To analyse the differences in the HH practice between known ESBL-E-carriers (use in ESBL-E-positive patient days) and patients not known to be ESBL-E-carriers (use in ESBL-E-negative patient days), AHC consumption in ESBL-E-positive and -negative patient days will be calculated separately at total and ward levels and by intervention period and differences will be tested.

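### The ESBL-E infection comparison pools patients who arrived as carriers with patients who arrived negative, so a ratio near 1 is expected even if contact isolation halves acquisition; synopsis and body also define the endpoint differently

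*Protocol*

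**What the plan says.** - **Endpoint.** Protocol 5.10.2 lists "New events of nosocomial ESBL-E infections expressed as incidence density of nosocomial ESBL-E-infections per 1000 patient days", with case definitions by modified CDC criteria. Carriage at admission plays no part in it.
- **Analysis.** Protocol 9.2.4: "The incidence density of hospital-acquired infections caused by ESBL-E in the CI period with the SP period will be compared in total and ward levels". A confounder-adjusted regression is added, but no split by admission carriage.
- **Contrast with the primary endpoint.** Protocol 5.10.1 counts acquisitions only "from patients with negative admission screening results".
- **Interpretation.** The synopsis presents the infection outcome as the efficacy of CI in "reducing the cumulative incidence of ESBL-E infections as determined by laboratory-based surveillance of clinical culture results". Both the measure and the way cases are found differ from 5.10.2.
- **Carriage.** Section 3 says that carriage among healthy people and people admitted to hospital "has risen sharply to 3-7 % depending on the setting and the population studied".
- **Data.** Section 6.3 (Data Form 3): "The following data will be only obtained from patients who are ESBL-E-positive". The form holds known carrier status at admission, days of admission and finding, sample results and daily infection status. Section 6.2 gives the daily ward census for all patients.

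**The concern.** The synopsis describes both strategies as meant to reduce transmission between patients. The direct route from CI to fewer infections is therefore through fewer acquisitions, in patients who arrived negative. The infection endpoint also counts infections in patients who brought the organism with them. If those patients are the majority of carriers, their infections dominate the count and dilute any effect that runs through transmission.

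Section 3 asks that the effect on clinical infections be examined before conclusions about isolation are drawn. A ratio close to 1 could be taken to show that CI does nothing for infection, when it would look much the same if CI had halved acquisition. Pooling can also hide opposite effects. Section 3 names side effects of isolation, such as reduced contact with physicians, and these would fall on the isolated carriers.

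**Working it through.** **The plan's own figure.** The documents give no figure for infections. The acquisition effect used below is the one the trial is sized on. A continuity-corrected comparison of 0.8% with 0.4% (two-sided 0.05, 80% power) gives 6,341 per phase, against 6,343 in section 9.1. Then 12,686 × 2.9 = 36,789, against 36,788.

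**Inputs**

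| Input | Value | Source |
|---|---|---|
| Carriers at admission, c | 3 to 7 per 100 | Section 3 |
| Acquisition under SP | 0.8 per 100 (stated as a minimum) | Section 9.1 |
| Acquisition under CI | 0.4 per 100 (50% reduction) | Section 9.1 |
| Patients per strategy | 19,764 (20 wards, one year) | Section 9.1 |
| Infection risk of an acquired carrier relative to an admission carrier, r | not given | Assumption, 0.5 to 2 |

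**Step 1: who the carriers are.** Admission carriers outnumber acquirers under SP by 3/0.8 = 3.75 to 7/0.8 = 8.75 times. Acquirers are 0.8/3.8 = 21% to 0.8/7.8 = 10% of all carriers.

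**Step 2: expected pooled ratio.** If CI halves acquisition and leaves infections in admission carriers unchanged, the CI/SP ratio is (c + 0.4r)/(c + 0.8r).

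| r | c = 3 | c = 7 |
|---|---|---|
| 0.5 | 3.2/3.4 = 0.94 | 7.2/7.4 = 0.97 |
| 1 | 3.4/3.8 = 0.89 | 7.4/7.8 = 0.95 |
| 2 | 3.8/4.6 = 0.83 | 7.8/8.6 = 0.91 |

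Among patients negative at admission the ratio is 0.4r/0.8r = 0.50 for any r, provided the admission screen misses no carriers.

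**Step 3: what moves it.** Acquisition counts only after day 3 of an assumed 10-day average stay, which leaves fewer days at risk and argues for r below 1. Acquisitions may also be found through clinical specimens, so some acquirers may be detected because they are infected, which argues for r above 1. Acquisition above 0.8 acts like a larger r: at 1.6 per 100 with r = 1, the ratio is again 3.8/4.6 = 0.83 to 7.8/8.6 = 0.91.

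**Step 4: precision, ignoring clustering.** Events for 80% power are 4 × (1.96 + 0.84)²/(ln ratio)². That is 66 at 0.50, about 2,550 at 0.895 and about 11,900 at 0.95.

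- At 3% carriage, carriers over both strategies number 2 × 593 + 158 + 79 = about 1,423. At 7% they number about 3,004. One infection in every carrier would still fall short of the pooled requirement.
- Acquirers number 158 + 79 = 237. Reaching 66 events would need 66/237 = 28% of them to be infected, and nothing in the documents supports a rate that high.
- With r = 1 the expected difference is the same in both analyses, but the restricted one drops the noise from admission carriers. Signal-to-noise rises by √(1,423/237) = 2.5 at 3% and √(3,004/237) = 3.6 at 7%.

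**The case against.** The strongest reply is that the pooled rate is a proper endpoint. CI is applied to whole wards, the stated objective is the incidence of nosocomial ESBL-E infection, and section 3 treats fewer infections as the real goal. If most infections arise in imported carriers, a ratio near 0.9 is the true total effect on the ward, not a bias. This stands. A reader might infer that the pooled endpoint is invalid and should become merely descriptive, but the documents do not support that. Doing so would also take the isolated patients, who bear any side effects, out of the formal comparison.

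A reader might also infer that CI cannot affect infections in patients who arrive as carriers. That is too absolute. Section 3 cites lower hand hygiene compliance under isolation, and section 4.2.2 makes hand hygiene towards known carriers under CI and SP a hypothesis. The observation SOP (5.2) accepts that glove and gown changes within one patient's care may affect infection prevention. An effect in either direction is possible, which is a reason to look at these patients separately.

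Three further points stand in part:

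- The documents give no infection risks, the 3-7% covers healthy people too, and 0.8 is a minimum. No single ratio can be claimed.
- The restricted comparison will probably also be imprecise.
- A split could appear in an SAP that is not shown. However, the protocol itself fixes the endpoint population, the comparison and the efficacy reading. The halved acquisition would show in the primary endpoint, but that does not answer the infection question.

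**Conclusion.** The point holds as one about interpretation and a missing component. On the protocol's figures, halving acquisition gives a pooled infection ratio of about 0.89 to 0.95 at equal infection risk per carrier, 0.94 to 0.97 at half the risk for acquirers and 0.83 to 0.91 at double. The corresponding ratio in patients negative at admission is 0.50. These values assume no effect of CI on infections in admission carriers and a complete admission screen. Over this range the dilution is strong, so a near-null pooled result cannot by itself show that CI prevents no infections through reduced transmission.

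The conflict between the synopsis and sections 5.10.2 and 9.2.4 over the measure, and between the synopsis and 5.10.2 over how cases are defined, rests on no assumption.

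**What to change.** 1. Keep the pooled CI versus SP comparison and label it the total ward-level effect.
2. Add to 5.10.2 and 9.2.4 a prespecified CI versus SP comparison of nosocomial ESBL-E infection density in patients not positive at admission, and compare infections in patients positive at admission as a separate stratum.
3. Take admission status from Data Form 3 and the screening results. State how the form's item on known carriage combines with the study screen. For patients not positive at admission, use census days minus the days of admission carriers as the denominator.
4. Reconcile the synopsis with 5.10.2 and 9.2.4 so that one measure and one case definition apply throughout.

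The cost is a wording change and a stratified analysis of data already planned. Each stratum will have few events and wide intervals, so the results should be presented as estimates, not confirmatory tests. The denominator for patients not positive at admission will include some unscreened patients. Any carriers among them, or missed by the screen, leave some dilution in that stratum.
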